A double-blind, randomized investigator-initiated study to determine the safety and the effect of Diamyd® in combination with Vitamin D on the progression to type 1 diabetes in children with multiple islet cell autoantibodies.

Study code: DiAPREV -IT 2

Phase IIa study

STATISTICAL ANALYSIS PLAN

Signatures:

Statistical Analysis Plan was prepared by:

Study Statistician
4Pharma Ltd

Date

Statistical Analysis Plan was reviewed/approved by:

Senior Statistician
4Pharma Ltd

Date

CEO, Diamyd Medical AB

Date

Principal Investigator

Date

Table of Contents

1	Abbreviations.....	4
2	Study objective(s).....	4
3	Design and type of the study	4
3.1	Randomization and blinding.....	4
4	Study variables	5
5	Sample size considerations.....	5
6	Statistical hypotheses.....	5
7	Analysis sets	6
7.1	Intention to Treat Population (ITT)	6
7.2	Full Analysis Population.....	6
7.3	Per protocol (PP) Population	6
7.4	Safety Population.....	6
8	General statistical considerations	6
9	Demographic and other baseline characteristics	6
10	Concomitant medication/treatment	6
11	Extent of exposure and compliance	7
12	Analysis of efficacy.....	7
12.1	Primary efficacy variables.....	7
12.2	Secondary efficacy variables.....	7
12.3	Subgroup analysis	7
12.4	Exploratory efficacy variables	8
13	Analysis of safety	8
13.1	Adverse events	8
13.2	Laboratory safety variables	8
13.3	Physical and neurological examination, vital signs	8
13.4	GADA titers, isotype, epitope and affinity, anti-idiotypic antibodies	9
13.5	Autoimmunity other than diabetes	9
13.6	Injection site reactions.....	9
14	Completion and premature discontinuation	9
15	Post diagnosis intervention and follow-up.....	9
16	Deviations from the analyses planned in the study protocol.....	9
17	Execution of statistical analyses.....	9
18	Hardware and software.....	9
19	References	9
20	Appendices	9
20.1	Schedule of assessments.....	10
20.2	Table and figure plan.....	11

1 Abbreviations

AE	Adverse Event
AUC	Area Under the Curve
BDR	Blind Data Review
DSMB	Data Safety Monitoring Board
FPIR	First-phase insulin response
HbA1c	Hemoglobin A1c
ITT	Intent to Treat
IvGTT	Intravenous Glucose Tolerance Test
OGTT	Oral Glucose Tolerance Test
PP	Per-protocol
SAE	Serious Adverse Event
SAP	Statistical Analysis Plan

2 Study objective(s)

The purpose of the study is to assess the safety and efficacy of Diamyd[®] 20 µg + vitamin D (2000 IU/day) in comparison with placebo + vitamin D (2000 IU/day) in non-diabetic children with multiple islet autoantibodies.

The primary objective of the study is to evaluate if Diamyd[®], in children treated with relatively high doses of vitamin D, may delay or stop the autoimmune process leading to clinical type 1 diabetes in children with ongoing persistent beta cell autoimmunity as indicated by multiple positive islet cell autoantibodies.

The secondary objective is to demonstrate that Diamyd[®] is safe in children at risk for type 1 diabetes.

3 Design and type of the study

This is a phase IIa, double-blind, randomized, placebo-controlled, parallel group single centre study in children with multiple islet cell autoantibodies with a maximum of two-year follow-up.

3.1 Randomization and blinding

Eligible participants were randomized to active treatment or placebo, with 1:1 ratio. This randomization was stratified by glucose metabolism at baseline applying the following categorisation:

- A) Impaired glucose metabolism defined as low first phase insulin response on IvGTT (≤ 30) and/or an increased 30, 60, 90 min glucose values (≥ 11.1 mmol/L) and/or 120 minutes glucose value (≥ 7.8 mmol/L) on OGTT, and/or HbA1c ≥ 39 and/or fasting glucose ≥ 6.1 mmol/L
- B) Normal glucose metabolism

An independent statistician performed the randomization procedure. The randomization code for each child was preserved in envelopes in a locked safe. The treating physician had the possibility to break the code in cases of emergency. Further the Data Safety Monitoring Board (DSMB) had the possibility to request access to the randomization list.

4 Study variables

The following variables will be evaluated.

The demographic and baseline variables:

Age, Gender, Height, Weight, HLA genotypes, First degree relative or from general population, Autoantibodies, Other autoimmune diseases (celiac disease, thyroid disease).

The primary efficacy variable:

Type I diabetes status after 2-year follow-up

The secondary efficacy variables:

Proportion of children who progress from normal to impaired glucose metabolism and proportion of children who progress from impaired to more severely impaired glucose metabolism

The exploratory efficacy variables:

C-peptide, oGTT/IvGTT, plasma glucose, HbA1c

The safety variable:

Adverse events (AE), safety laboratory, physical and neurological examination, vital signs, GADA titers, isotype, epitope and affinity, anti-idiotypic antibodies, injection site reactions

5 Sample size considerations

The planned sample size of the study was 80 children, 40 in each of the study arms. This sample size was based on the expectation that 50% of the untreated children with multiple autoantibodies will develop type 1 diabetes within 5 years. This frequency had previously been reported equal among relatives to diabetes patients and in the general population. If 20% of the treated children would develop type 1 diabetes within the same period of time, there would have been a power of 82% with $\alpha=5\%$ with a group of $40+40=80$ children. P value <0.05 was to be used as the significance level.

However, the study was stopped prematurely ending up with a total sample size of 29 children. The study was stopped due to negative results received from another similar study (DiAPREV/2008). In that study no effect on delaying or preventing type 1 diabetes with Diamyd[®]-treatment was shown, while GADA increased in the study patients. Since the cohort of children, inclusion and exclusion criteria and dose of Diamyd[®] were all equal in DiAPREV/2008 and DiAPREV-IT 2, it is not probable that the current study would show that Diamyd[®] would delay or prevent type 1 diabetes, but it may have effects on the immune system that can be explored in mechanistic studies.

6 Statistical hypotheses

As the study was stopped prematurely with limited number of children within both treatment arms, no formal statistical hypotheses are defined.

7 Analysis sets

The database will be reviewed in a blinded manner prior to database lock. Patients are assigned to the respective analysis sets depending on the observed protocol violations.

7.1 Intention to Treat Population (ITT)

The ITT-population comprises all randomized (as planned) subjects.

7.2 Full Analysis Population

The Full Analysis Set (FAS) is a subset of ITT and comprises of all subjects who received any study drug and who participated in at least one post-baseline assessment. FAS is the primary efficacy population.

7.3 Per protocol (PP) Population

The PP population comprises of all subjects who did not substantially deviate from the protocol as to be determined on a per-subject basis. The PP population is used for sensitivity purposes.

7.4 Safety Population

The Safety Population comprises of all subjects who received at least one administration of the study drug at any dosage.

8 General statistical considerations

Descriptive statistics include at least the number of participants, mean, standard deviation (SD), minimum, median and maximum for continuous variables, and frequencies and percentages for categorical variables. Line listings of all participants are provided as well.

Missing values will not be imputed in the analyses.

The table and figure plan is presented in Appendix 18.2.

9 Demographic and other baseline characteristics

All background and other baseline characteristics will be tabulated with descriptive statistics. Medical history will be summarized with frequency distributions including both event and subject counts. Tabulations will be conducted by treatment group. No statistical tests will be carried out for any baseline measures between the treatments.

10 Concomitant medication/treatment

Concomitant medication and treatments will be summarized overall and by treatment group using ATC classification.

11 Extent of exposure and compliance

The extent of exposure and treatment compliance will be summarized descriptively overall and by treatment group.

12 Analysis of efficacy

Descriptive statistics of all the efficacy data will be presented by visit and treatment group. ITT-population will serve as the primary efficacy population.

12.1 Primary efficacy variables

The primary efficacy variable is the type 1 diabetes status (with vs without type 1 diabetes) at the end of the two-year follow-up. The proportion of children developing clinical type 1 diabetes during the two-year follow-up will be summarized with frequency tables. The proportions of children with type 1 diabetes will also be summarized for other study visits by treatment group. The analysis will be conducted for both ITT and PP populations.

In addition, time to the development of type 1 diabetes up to 2 years will be graphically illustrated by Kaplan-Meier curves by treatment.

12.2 Secondary efficacy variables

The secondary efficacy variables are the proportion of children who have progression from normal to impaired glucose metabolism (within children with normal glucose metabolism at screening) and the proportion of children who have progression from already impaired glucose metabolism from one or several criteria to additional signs of reduced glucose metabolism (within children with impaired glucose metabolism at screening).

Impaired glucose metabolism is defined as acceptance of at least one of the following criterion; a) F-glucose ≥ 6.1 mmol/L, b) maximum p-glucose at 30, 60, 90 minutes ≥ 11.1 mmol/L in the OGTT, c) 120 min p-glucose ≥ 7.8 mmol/L on OGTT, d) HbA1c ≥ 39 mmol/mol.

Both the secondary efficacy variables will be summarized descriptively by visit and treatment group.

12.3 Subgroup analysis

Subgroup analysis will be conducted for the primary and secondary efficacy variables, so that the above-mentioned analyses will also be assessed by HLA genotype (DR3-DQ2, present/absent). The DR3-DQ2 subgroup will be derived from the database so that patients that have HLA-DQ haplotype of DQ2 (DQ2/8 or DQ2/x) are classified as DR3-DQ2 (present) and the ones without DQ2 (DQ2.2/8; DQ8/8 or DQ8/x) are classified as DR3-DQ2 (absent).

12.4 Exploratory efficacy variables

The exploratory efficacy variables include

- 1) first-phase insulin response (FPIR) and K-value from IvGTT
- 2) fasting, maximum, 2 hours and AUC_{0-120min} C-peptide levels from OGTT,
- 3) fasting, maximum, 2 hours and AUC_{0-120min} plasma-glucose from OGTT,
- 4) HbA1c (mmol/mol),
- 5) Fasting and AUC_{0-120min} insulin levels from OGTT,
- 6) AUC_{90min} of C-peptide, glucose and insulin from IvGTT

All the exploratory efficacy variables will be summarized descriptively including both the absolute and change from baseline values by visit and treatment group if feasible. In addition, the endpoints will be illustrated graphically if feasible.

The AUC values for C-peptide, plasma glucose and insulin will be calculated applying linear trapezoidal rule. In case of single missing time points for the C-peptide/plasma-glucose/insulin are detected, it will be assumed that missing values fall linearly between existing data points. In case the 0 min timepoint is missing, the corresponding AUC is set to missing.

13 Analysis of safety

All safety analyses will be conducted for the Safety population.

13.1 Adverse events

All adverse events (AEs) will be tabulated (according to the MedDRA dictionary) by treatment group, system organ class (SOC), preferred term (PT), severity and causality. Both participant and event counts will be calculated. For participants with more than one occurrence of the same preferred term, the strongest causality and severity will be used when participant counts are reported.

In addition, serious adverse events (SAE) and adverse events leading to discontinuation will be reported separately.

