20.1 Schedule of assessments

Event	Visit 0 Information and consent	Visit 1 Day 1 30 +/- 7 days from visit 0	Visit 2 Month 1 30 +/-7 days from visit 1	Visit 3 Month 3 3 months +/- 14 days from visit 1	Visit 4 Month 6 6 months +/- 14 days from visit 1	Visit 5 Month 9 9 months +/- 14 days from visit 1	Visit 6 Month 12 12 months +/- 14 days from visit 1	5 Years Follow up Every 3 rd or 6 th month Every visit +/- 14 days from visit 1
Informed Consent	X							
Randomization		X						
Diamyd/Placebo Administration		X	X					
Start of Vitamin D	X							
Medical History	X							
General Physical Exam	X	X	X	X	X		X	Last visit
Concomitant Medication	X	X	X	X	X		X	Every 6 th month
Weight, Height	X	X	X	X	X		X	Every 6 th month
Vital signs (BP)	X	X	X	X	X		X	Every 6 th month
Blood Sampling:								
Hematology, chemistry, including calcium	X	X	X	X	X	X	X	Every 3 rd month
25 OH-vitamin D3	X	X			X		X	Every 6 th month
Cellular analyses	X		X		X		X	Every 6 th month
GADA, IA-2A, ZnT8A, IAA	X	X	X	X	X	X	X	Every 3 rd month
C-peptide	X Fasting + stimulated	X Fasting + stimulated	X Random	X Random	X Fasting + stimulated	X Random	X Fasting + stimulated	Every 6 th month Fasting + stimulated
HbA1c	X	X	X	X	X	X	X	Every 3 rd month
Plasma Glucose	X	X	X	X	X	X	X	Every 3 rd month
OGTT/IvGTT	IvGTT	OGTT			OGTT		IvGTT	Every 6 th month IvGTT/OGTT
TPOAb, ThglAb, tTGAb	X						X	Every 12 th month
Urine Analysis	X	X	X	X	X		X	Every 6 th month
Neurological Assessment	X		X	X	X		X	Last visit
Injection Site Inspection		X	X	X	X			
Adverse Events		X	X	X	X		X	Last visit
Diary		X	X	X	X		X	Last visit
Questionnaire to child about the study procedures		X						Last visit

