14.2.3 Exploratory efficacy analyses

Table 14.2.3.1	Descriptive statistics of first-phase insulin response (FPIR) and K-value from IvGTT by treatment and visit (ITT)
Table 14.2.3.2	Change from baseline in first-phase insulin response (FPIR) and K-value from IvGTT by treatment and visit (ITT)
Table 14.2.3.3	C-peptide concentrations from OGTT by treatment, visit and timepoint (ITT)
Table 14.2.3.4	Maximum and AUC0-120min C-peptide values from OGTT by treatment and visit (ITT)
Table 14.2.3.5	Change from baseline in fasting, maximum and 2 hours C-peptide (OGTT) by treatment, visit and timepoint (ITT)
Table 14.2.3.6	P-glucose concentrations from OGTT by treatment, visit and timepoint (ITT)
Table 14.2.3.7	Maximum and AUC0-120min P-glucose values from OGTT by treatment and visit (ITT)
Table 14.2.3.8	Change from baseline in fasting, maximum and 2 hours P-glucose (OGTT) by treatment, visit and timepoint (ITT)
Table 14.2.3.9	HbA1c concentrations by treatment, visit and timepoint (ITT)
Table 14.2.3.10	Change from baseline in HbA1c concentration by treatment, visit and timepoint (ITT)
Table 14.2.3.11	Insulin concentrations from OGTT by treatment, visit and timepoint (ITT)
Table 14.2.3.12	Maximum and AUC0-120min Insulin values from OGTT by treatment and visit (ITT)
Table 14.2.3.13	Change from baseline in fasting and maximum Insulin concentration (OGTT) by treatment, visit and timepoint (ITT)
Table 14.2.3.14	C-peptide concentrations from IvGTT by treatment, visit and timepoint (ITT)
Table 14.2.3.15	AUC0-90min C-peptide values from IvGTT by treatment and visit (ITT)
Table 14.2.3.16	Glucose concentrations from IvGTT by treatment, visit and timepoint (ITT)
Table 14.2.3.17	AUC0-90min Glucose values from IvGTT by treatment and visit (ITT)
Table 14.2.3.18	Insulin concentrations from IvGTT by treatment, visit and timepoint (ITT)
Table 14.2.3.19	AUC0-90min Insulin values from IvGTT by treatment and visit (ITT)

14.3	Safety
14.3.1	Adverse events
Table 14.3.1.1	Summary of adverse events (Safety)
Table 14.3.1.2	Adverse events by SOC and PT (Safety)
Table 14.3.1.3	Adverse events by SOC, PT and severity (Safety)
Table 14.3.1.4	Adverse events by SOC, PT and causality (Safety)
Table 14.3.1.5	Serious adverse events (Safety)
Table 14.3.1.6	Adverse events leading to discontinuation (Safety)
14.3.2	Laboratory safety variables
Table 14.3.2.1	Summary of safety laboratory - Hematology (Safety)
Table 14.3.2.2	Summary of safety laboratory - Clinical chemistry (Safety)

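### No adverse event table is split by onset, so a non-local acute reaction to the two early injections is pooled with up to two years of background events

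*SAP*

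**What the plan says.** **Tabulation.** SAP section 13.1 presents adverse events "by treatment group, system organ class (SOC), preferred term (PT), severity and causality". It adds that "Both participant and event counts will be calculated". The rule for repeats is: "For participants with more than one occurrence of the same preferred term, the strongest causality and severity will be used". The end of the same sentence sets its scope: "the strongest causality and severity will be used when participant counts are reported". The strongest-grade rule is therefore confined to the participant counts. Serious events and events leading to discontinuation are reported separately. In the table plan (section 20.2), Tables 14.3.1.1 to 14.3.1.6 follow this layout, and none has a visit, period or onset dimension.

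**Schedule.** In section 20.1 the row "Diamyd/Placebo Administration" is marked at Visit 1 (Day 1) and Visit 2 (Month 1) only. The row "Adverse Events" is marked at Visits 1, 2, 3, 4 and 6, not at Month 9, and in the follow-up column only at the last visit. Section 3 describes the study as one "with a maximum of two-year follow-up".

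**Other safety data.** Laboratory values, vital signs, examination findings and antibodies are summarised by visit and arm (sections 13.2 to 13.4). Injection site reactions are summarised by severity, visit and arm (section 13.6), with separate pre- and post-injection tables (14.3.6.1 and 14.3.6.2). An adverse event listing is planned (Listing 16.2.6).

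**The concern.** The product is given twice, one month apart, at the start of a follow-up that may last two years. An acute effect would fall in the first weeks. The planned tables combine those weeks with all later ordinary childhood illness, and nothing in them separates the two.

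The local reactions are covered elsewhere. What is left is the non-local reaction with a common term, such as fever or headache. It appears only in the general adverse event tables, where background events of the same term accumulate in both arms. The participant count is affected twice. A child who would have had the term anyway at some point in two years does not add to the arm difference by also having it after an injection. If a later episode is worse, the child is shown at the later severity. The event count retains the early event but places it among many unrelated ones.

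This matters because safety is the secondary objective (section 2) and section 6 defines no formal hypotheses. The descriptive tables are the safety comparison.

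**Working it through.** The SAP states no adverse event rate, so there is no figure of the plan to reproduce. The mechanism can be shown only on assumed inputs.

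**Inputs from the SAP**
- 29 children (section 5), randomised 1:1 (section 3.1)
- Follow-up of at most two years (section 3)
- Injections at Day 1 and Month 1, and Visit 3 at Month 3 (section 20.1)

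**Assumptions**
- 15 Diamyd v 14 placebo children, since the actual split is not given
- Every child followed for the full two years
- A background of r = 0.2, 0.5 or 1.0 events per child-year for one term, constant over time and equal in both arms
- An acute excess of a = 20% of Diamyd children with one extra event, all before Month 3
- First injection to Visit 3 taken as T = 0.25 years

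**Participant counts**

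Placebo: p0 = 1 − exp(−rT). Diamyd: p1 = 1 − (1 − a)(1 − p0). The difference is therefore a × exp(−rT).

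| r per year | Two years: difference | To Month 3: difference |
|---|---|---|
| 0.2 | 0.2 × exp(−0.4) = 13 points | 0.2 × exp(−0.05) = 19 points |
| 0.5 | 0.2 × exp(−1.0) = 7 points | 0.2 × exp(−0.125) = 18 points |
| 1.0 | 0.2 × exp(−2.0) = 3 points | 0.2 × exp(−0.25) = 16 points |

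Central case, r = 0.5:
- Two years: p0 = 1 − exp(−1) = 63% and p1 = 1 − 0.8 × 0.368 = 71%. SE = √(0.706 × 0.294/15 + 0.632 × 0.368/14) = 0.175, so difference/SE = 0.074/0.175 = 0.4.
- To Month 3: p0 = 1 − exp(−0.125) = 12% and p1 = 1 − 0.8 × 0.882 = 29%. SE = √(0.294 × 0.706/15 + 0.118 × 0.882/14) = 0.146, so difference/SE = 0.176/0.146 = 1.2.

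**Event counts, r = 0.5**
- Two years: 15 × (0.5 × 2 + 0.2) = 18.0 v 14 × (0.5 × 2) = 14.0. The per-child ratio is 1.2/1.0 = 1.2.
- To Month 3: 15 × (0.125 + 0.2) = 4.9 v 14 × 0.125 = 1.8. The per-child ratio is 0.325/0.125 = 2.6.
- The excess is 15 × 0.2 = 3 events in both cases. It is not lost from the two-year event count, but it stands out less.

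**Sensitivity to follow-up.** With one year instead of two and r = 0.5, the participant difference is 0.2 × exp(−0.5) = 12 points rather than 7. Shorter follow-up means less dilution.

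**Severity rule, by reasoning.** Take a child with a mild fever on Day 2 and a severe fever in Month 15. The event count by severity shows one mild and one severe event. The participant count in Table 14.3.1.3 shows one child at severe, and the early mild episode cannot be seen there.

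**The case against.** The other side has a good deal on its side.

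- **Event counts are planned.** A reader might infer that a Day 2 fever adds nothing once the same child has a fever in Month 15. That is not so: the event count rises by one. But event counts are not split by onset either, so the early event cannot be told from the later one.
- **The strongest-causality rule protects the early event.** If the early fever is judged related and the late one unrelated, the child is counted as related in Table 14.3.1.4, and the judgement is made in a double-blind trial. This mitigates the problem. It remains an individual judgement and does not replace a comparison by onset.
- **Local reactions are time-resolved.** A reader might infer that the plan cannot show acute injection reactions at all. Sections 13.6 and 20.2 say otherwise, but those tables name only local signs and symptoms such as erythema, tenderness and itching.
- **The listing covers only 29 children.** A reviewer can read onset there if dates are shown, though a listing is not a comparison of arms.
- **Whole-study tables are conventional.** They also have a purpose here, because vitamin D starts at Visit 0 and is common to both arms (sections 2 and 20.1). Nothing in section 13.1 is wrong in itself, and the strongest-grade rule does not cause the pooling. The cause is the missing onset dimension.
- **The size is assumed.** The study stopped early and two years is a maximum. Late events may also be under-recorded. Either would reduce the dilution.

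One further inference should be resisted: that the second year rests on a single retrospective enquiry. The schedule does mark adverse event review after Month 12 only at the last visit, but it marks the diary there too. The reporting rules belong to the protocol, which is not shown.

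**Conclusion.** The point holds in a limited form. No planned adverse event table separates the weeks around the two injections from the rest of follow-up. The consequence is confined to non-local acute reactions with common terms. For these, both kinds of count are diluted, and in the participant counts a worse late episode overwrites the early severity.

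Over the assumed background range of 0.2 to 1.0 events per child-year, the participant difference is 13 to 3 points over two years against 19 to 16 points to Month 3. Dilution is small for rare terms and large for very common ones. These figures illustrate the mechanism and do not estimate what this trial will show. Even to Month 3, the central difference is only about 1.2 standard errors, so with 29 children any onset split is descriptive. The documents do not support calling the strongest-grade rule an error or saying that acute reactions are invisible. Severity is low: a cheap improvement to the safety reporting.

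**What to change.** In Tables 14.3.1.2 (SOC and PT) and 14.3.1.3 (severity), add descriptive columns by onset: first injection to Visit 3 (Month 3), which covers both injections, and after Visit 3. In each period:

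- give both participant and event counts;
- apply the strongest-severity rule within the period;
- use the children under observation in that period as the denominator.

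Keep the all-period column. Add a footnote that the schedule marks adverse event review after Month 12 only at the last visit, so that the later column is read with that in mind. State the change in section 13.1.

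The cost is a sentence or two in the SAP and slightly longer tables. No new data are needed, provided that onset dates were recorded, which is assumed here. No test is added, in keeping with section 6.
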